4.1.3 Baseline and Change from Baseline

Baseline is defined as last non-missing observation before or on date of successful insertion

- Change from baseline (CHG)= post-baseline value – baseline
- Percent change from baseline = $100.0 \times \text{CHG}/\text{Baseline}$

4.1.4 Analysis Windows

For analysis purposes, early termination visits and unscheduled follow-up visits will be assigned analysis visits according to the analysis windows in the following table. This mapping applies to labs, vital signs, and all other data planned to be collected and analyzed by visit in the Study Data Tabulation Model (SDTM) finding domains. Where multiple measurements for a particular parameter appear within an analysis window, the result closest to target day will be used. If equidistant, the latter result will be used for the summary measure. All measures may not be used in the data summaries (e.g., 2 vital signs measures within the same analysis visit window), but all measurements will appear in the datasets and listings.

Table 4.1.4.1 Analysis Windows:

Scheduled Visit (Subject Visit Window)	Analysis Visit	Analysis Window Target Day	Analysis Window	
			Lower Bound	Upper Bound
Visit 1/Screening	Baseline	1	N/A	1
Visit 2 (Day 1)				
Visit 3 (Day 3± 24 hours)	Day 3	3	2	5
Visit 4 (Day 8± 1 day)	Day 8	8	6	11
Visit 5 (Day 15± 1 day)	Day 15	15	12	18
Visit 6 (Day 22± 1 day)	Day 22	22	19	25
Visit 7 (Day 29± 1 day)	Day 29	29	26	43
Visit 8 (Day 57± 3 days)	Day 57	57	44	120
Visit 9 (Month 6± 30 days)	Month 6	182	121	273
Visit 10 (Month 12± 30 days)	Month 12	364	274	456
Visit 8 (Month 18± 1 month)	Month 18	548	457	639
Visit 9 (Month 24± 1 month)	Month 24	730	640	822
Visit 10 (Month 30± 1 month)	Month 30	913	823	1004
Visit 12 (Month 36± 1 month)	Month 36	1095	1005	1278
Visit 14 (Month 48± 1 month)	Month 48	1460	1279	1642
Visit 16 (Month 60± 1 month)	Month 60	1825	1643	N/A

4.1.5 Exposure Periods

The first exposure cycle starts on Day 1 of successful study device insertion. A full exposure cycle is comprised of 28 days. One woman-year comprises thirteen 28-day cycles. The following exposure periods are defined for analysis in terms of planned study days and study cycles to facilitate the efficacy and certain safety analyses.

Exposure Period	Study Day of Period Start (PSTDY)	Study Day of Period End (PENDY)
Year 1 (Cycle 1- Cycle 13)	1	364
Year 2 (Cycle 14-Cycle 26)	365	728
Year 3 (Cycle 27-Cycle 39)	729	1092
Year 4 (Cycle 40-Cycle 52)	1093	1456
Year 5 (Cycle 53-Cycle 65)	1457	1820
First 2 Years (Cycle 1-Cycle 26)	1	728
First 3 Years (Cycle 1-Cycle 39)	1	1092
First 4 Years (Cycle 1-Cycle 52)	1	1456
5 Years (Cycle 1-Cycle 65)	1	1820

Type of Events and Study Day During an Exposure Period

ETYPE	Event	Study Day of Event (EVTDY)
A	Expulsion	Study Day of Expulsion date
B	Expulsion followed by conception within 7 days	Study Day of Expulsion date
C	Removal	Study Day of Removal date
D	Removal followed by conception within 7 days	Study Day of Removal date
E	Pregnancy before expulsion	Study Day of Conception date
F	Pregnancy before removal	Study Day of Conception date
H	Lost to follow-up without pregnancy, expulsion, or removal	Study Day of Last Date Device in Situ
I	Complete period without pregnancy, expulsion, or removal	Study Day of Period End Date

Note: Removal due to partial expulsion will be treated as expulsion

Exposure Duration in Days (EXDUR):

if EVTDY-PSTDY>0 then EXDUR = min(EVTDY-PSTDY+1, PENDY-PSTDY+1);
 else EXDUR=.;

Exposure Duration in Cycles (NCYCF) = EXDUR/28

Number of Completed Cycles (NCYCC) = INT(NCYCF)

Number Relevant Cycles (NCYCR)

=NCYCC+1 if last partial cycle is \geq 23 days
 =NCYCC+1 if last partial cycle ETYPE is B, D, E, or F
 =NCYCC, otherwise.

Number of Evaluable Cycles (NCYCEV) =NCYCR

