4. SELECTION OF STUDY POPULATION

4.1. Inclusion Criteria

A subject will be eligible for inclusion in this study if they *meet all of the following criteria:*

1. Post-menarcheal, pre-menopausal females up to 45 years of age at the time of informed consent/assent and in good general health;
2. History of regular menstrual cycles defined as occurring every 21-35 days when not using hormones or prior to recent pregnancy or spontaneous or induced abortion;
3. Sexually active with a male partner who has not had a vasectomy;
4. Reasonably expect to have coitus at least once monthly during the study period;
5. In a mutually monogamous relationship of at least 3 months duration;
6. Seeking to avoid pregnancy for the duration of the study;
7. Willing to use the study drug as the sole form of contraception;
8. Willing to accept a risk of pregnancy;
9. Subjects must be in compliance with cervical cancer screening guidelines per the American Society for Colposcopy and Cervical Pathology (ASCCP) guidelines without evidence of disease. Subjects who are age 21-24 y/o, at time of informed consent, must have a normal papanicolaou test (Pap), atypical squamous cells of undetermined significance (ASC-US), or low-grade squamous intraepithelial lesion (LSIL). Subjects who are 25 or older at the time of informed consent with ASC-US results, must also have a negative high risk human papilloma virus (HPV) test result within the appropriate screen timeframe per American Society for Colposcopy and Cervical Pathology (ASCCP) guidelines, and prior to the study IUD insertion. Alternatively, the subject must have had a colposcopy performed within the appropriate screen timeframe, and prior to the study IUD insertion that showed no evidence of dysplasia requiring treatment per ASCCP guidelines, or treatment was performed and follow-up at least 6 months after the treatment showed no evidence of disease by clinical evaluation;
10. Able and willing to comply with all study tests, procedures, assessment tools and follow-up;
11. Able and willing to provide and document informed consent and Authorization for Release of Protected Health Information (PHI). Unemancipated subjects under 18 years old must provide assent and have written parental consent documented on the consent form consistent with local legal requirements;
12. Plan to reside within a reasonable driving distance of a research site for the duration of the study.
13. Subject agrees not to self-remove VeraCept.

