5.5.2. Concomitant Therapy

All prescription and non-prescription medications (including herbal therapies) taken from the time of informed consent/assent until Study Exit must be documented in the source documents and CRF (brand and/or generic name, dose, dosing frequency, start and stop dates).

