6.1.3. Day 3 (48 hours (\pm 24 hours) post-insertion)

- Vital signs and weight
- 48-hour (\pm 24 hours) post IUD insertion PK sample collection
- Prior and concurrent medication
- Adverse events
- Subject education including:
 - Concomitant contraception - if there are concerns that the IUD is not properly placed, counsel the subject on the need for additional contraception

6.1.4. Days 8, 15, 22, 29 (\pm 1 day) and 57 (\pm 3 days)

- Vital signs and weight
- PK sample collection (at approximately the same time of day as collection of the Day 3, 48-hr PK collection)
- Pelvic exam to confirm IUD placement/string check
- Transvaginal ultrasound, if clinically indicated to confirm adequate IUD placement
- Prior and concurrent medication
- Adverse events
- Subject education including:

- Concomitant contraception - if there are concerns that the IUD is not properly placed, counsel the subject on the need for additional contraception
- **ParaGard Subjects:** Day 57 (± 3 days)
 - Exit Visit procedures should be completed as described in Section 6.1.6.

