6.1.5. Months 6, 12, 18, 24, 30, 36, and 48 (± 30 days)

- Vital signs and weight
- PK sample collection
- Pelvic exam to confirm IUD placement/string check
- Transvaginal ultrasound, if clinically indicated to confirm adequate IUD placement
- Prior and concurrent medication
- Adverse events
- Subject education including:
 - Concomitant contraception - if there are concerns that the IUD is not properly placed, counsel the subject on the need for additional contraception

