4.1.6 Pearl Index

Pearl Index is defined as the number of on-treatment pregnancies per 100 women years. On -treatment pregnancy is defined as the estimated conception date being on or after the insertion date (must be a successful insertion) and no more than 7 days after the study device is removed or expelled. One women year is defined as comprising thirteen 28-day cycles.

$$\text{Point estimate of Pearl Index: } x \times \frac{1300}{E}$$

where x is the number of on-treatment pregnancies and E is the number of 28-day evaluable exposure cycles

If ETYPE is B or D or E or F, then PREGNANCY = 1; else PREGNANCY = 0

x = sum of PREGNANCY

E = Number of Evaluable Cycles (NCYCEV)

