4.8 Pearl Index Analysis

The pearl index will be utilized to measure contraceptive efficacy through 5 years of use and will be analyzed using the Pearl Index with a 95% CI for women in the EP population. A separate summary of the Pearl Index in the EP Population through Day 57 will also be provided.

The Pearl Index is defined as the number of on-treatment pregnancies per 100 women years. On-treatment pregnancy is defined as the estimated conception date being after the insertion date and no more than 7 days after the VeraCept is removed or expelled. One woman year is defined as comprising thirteen 28-day cycles.

$$\text{Point estimate of Pearl Index: } x \times \frac{1300}{E}$$
$$95\% \text{ CI: } \left(\frac{1}{2} \chi^2_{(0.025, 2x)} \times \frac{1300}{E}, \frac{1}{2} \chi^2_{(0.975, 2(x+1))} \times \frac{1300}{E} \right)$$

where x is the number of on-treatment pregnancies, E is the number of 28-day evaluable exposure cycles, and $\chi^2_{(p, df)}$ is the p th quantile of χ^2 -distribution with df degrees of freedom.

x =sum of PREGNANCY

E =number of Evaluable Cycles (NCYCEV)

Pearl Index point estimates and 95% CIs will be calculated for Day 57, Years 1, 2, 3, 4, 5, Years 1-2, Years 1-3, Years 1-4, and for Years 1-5 separately.

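### The Pearl Index denominator keeps cycles in which another contraceptive was also used, which can only lower the index; the effect is probably small, and a short change to the SAP would address it

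*SAP*

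**What the plan says.** Safety SAP 4.1.5 counts completed 28-day cycles from exposure days. It adds one cycle if the last partial cycle has at least 23 days, or, for pregnancy-type events, "NCYCC+1 if last partial cycle ETYPE is B, D, E, or F". The result is the number of relevant cycles (NCYCR). The next line reads "Number of Evaluable Cycles (NCYCEV) =NCYCR".

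Section 4.1.6 then defines the index as x × 1300 / E, "where x is the number of on-treatment pregnancies and E is the number of 28-day evaluable exposure cycles". Section 4.8 gives its purpose: "The pearl index will be utilized to measure contraceptive efficacy through 5 years of use". It is reported with 95% limits for Day 57, for each of Years 1 to 5, and cumulatively. Section 4.9 promises counts of both relevant and evaluable cycles. Section 5 describes the index as based on *safety cycles*, a term that is not defined.

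On other contraception, the protocol says:

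- Inclusion criterion 7 is "Willing to use the study drug as the sole form of contraception", which is a statement of willingness at entry.
- Sections 6.1.2 to 6.1.5 tell staff, after placement on Day 1 and at each later visit through Month 48, "if there are concerns that the IUD is not properly placed, counsel the subject on the need for additional contraception".
- Section 5.5.3 prohibits oral contraceptives containing estrogen or progestogens. Condoms are not listed.
- Section 5.5.2 requires dated records of medicines: "All prescription and non-prescription medications (including herbal therapies) taken from the time of informed consent/assent until Study Exit must be documented".

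**The concern.** The SAP names two quantities and makes them identical, so the word *evaluable* carries no condition. A cycle covered by a second method says little about device failure, yet it adds a full cycle to E. Backup use that follows the protocol's own counselling is not a deviation. The exclusion in safety SAP 4.2.1 for major violations would therefore not naturally reach it, and that exclusion removes whole women rather than cycles.

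The index is the only contraceptive-efficacy measure in the plan. This flaw works in one direction, in favour of VeraCept, and the counselled cycles come from women whose device position was questioned.

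**Working it through.** **The plan's own figures.** The plan states no Pearl Index value, target or cycle total. Its exposure table reproduces: 13, 26, 39, 52 and 65 cycles × 28 days = 364, 728, 1,092, 1,456 and 1,820 days. Under 4.1.5 a woman with five full years in place contributes 65 evaluable cycles whatever other contraception she used.

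**Inputs.**

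- Planned VeraCept women: 20 (safety SAP 3.2; 12 / (1 − 0.40) = 20).
- Maximum cycles without replacements: 20 × 65 = 1,300 over five years. The age limit of 35 for the evaluable-for-pregnancy population makes the actual number lower.
- Day 57 index: 4.1.5 gives no exposure period for it. Taking 57 days, 57 / 28 = 2.04, so 2 cycles per woman and about 20 × 2 = 40 cycles at most.
- f, the removed cycles as a share of E, all of them non-conception cycles. **This is an assumption; the documents give no value.** Range shown: 1% to 20%.

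**Formulas** (safety SAP 4.8).

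- Estimate: x × 1300 / E.
- Lower limit: ½ χ²(0.025, 2x) × 1300 / E, which is 0 when x = 0.
- Upper limit: ½ χ²(0.975, 2(x + 1)) × 1300 / E.

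Replacing E by E(1 − f) divides each of these by (1 − f).

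**Years 1 to 5, E = 1,300.**

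| f | E after removal | x = 0: upper limit | x = 1: estimate | x = 1: upper limit |
|---|---|---|---|---|
| 0 (as planned) | 1,300 | 3.69 | 1.00 | 5.57 |
| 1% | 1,287 | 3.73 | 1.01 | 5.63 |
| 5% | 1,235 | 3.88 | 1.05 | 5.86 |
| 10% | 1,170 | 4.10 | 1.11 | 6.19 |
| 20% | 1,040 | 4.61 | 1.25 | 6.96 |

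With x = 0 the estimate and lower limit are 0 in every row. With x = 1 the lower limit is 0.03 throughout, to two decimals.

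**The same number of cycles in a long and a short window.** Suppose 4 cycles had backup use.

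- Years 1 to 5, x = 1: 1300 / 1300 = 1.000 becomes 1300 / 1296 = 1.003.
- Day 57, about 40 cycles: 4 / 40 = 10%. With x = 1, 1300 / 40 = 32.5 becomes 1300 / 36 = 36.1. With x = 0, the upper limit 3.689 × 1300 / 40 = 119.9 becomes 3.689 × 1300 / 36 = 133.2.

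The early window is the more exposed one. Seven of the counselling points (Days 1, 3, 8, 15, 22, 29 and 57) fall inside it.

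**Whether another rule removes these cycles.** Criterion 7 is checked at entry only. Section 5.5.3 covers oral hormonal methods but not barrier methods. Section 4.2.1 acts on subjects and requires a major violation. No section of either document drops a cycle.

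**The case against.** The other side has real weight.

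- **Counselling is conditional.** It applies only when placement is in doubt, and counselling is not the same as use. From Day 8 the same visits include a string check, and removal of a partly expelled device counts as expulsion and ends exposure. A reader might infer from the repeated visit item that backup use is routine, or that 5% to 20% of cycles are affected. The documents support neither. This stands.
- **The interval is far wider than the bias.** With one pregnancy in 1,300 cycles it runs from 0.03 to 5.57. The index is not a protocol endpoint, and safety SAP 4.10 says there is no formal efficacy analysis. This stands and sets the severity.
- **The data may not exist.** Section 5.5.2 requires dates for medicines. In both schedules the concomitant-contraception row is marked only at Day 1 and at Month 60 or Exit; at exit, contraception is supplied for use after removal. An e-diary appears only in a footnote to the safety SAP's Table 1. A reader might infer that use can be recovered for every cycle; for barrier methods the documents do not show that. This stands, and it limits what the fix can do.
- **Some use may already be handled.** Prohibited oral hormonal use could lead to exclusion under 4.2.1. This is partly right, but it does not cover use that follows the counselling.
- **All-cycle counting may be intended.** Section 5 refers to *safety cycles*. The term is undefined, and 4.1.6 and 4.8 call the cycles evaluable, so this does not settle the matter.
- **NCYCR also omits final partial cycles under 23 days without pregnancy**, which lowers E. That is a separate rounding rule, and it also counts partial cycles of 23 days or more as whole. It is no correction for backup use.

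**Conclusion.** The point holds, at minor severity. Evaluable cycles equal relevant cycles by definition, nothing removes a cycle with another contraceptive, and the resulting error can only favour VeraCept. Reported values are (1 − f) times the corrected ones. With no pregnancies only the upper limit is affected, so it would be wrong to say that the estimate and both limits are always too low.

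The size rests entirely on f, which is not in the documents. It may be negligible over five years and could be noticeable in the Day 57 index. A reader might go further and conclude that VeraCept's efficacy will be materially overstated. The documents do not support that: they give no frequency of backup use, no target for the index and no decision that depends on it.

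**What to change.** In safety SAP 4.1.5, define NCYCEV as NCYCR minus the 28-day cycles in which use of another contraceptive is recorded with dates in the study data. Examples are hormonal, emergency or spermicide entries on the concomitant-medication page, and barrier use where it was captured. Keep every cycle in which conception occurred. Use this NCYCEV as E in 4.1.6 and 4.8.

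Report the all-cycle index (E = NCYCR) beside it, labelled as the *safety cycles* index of Section 5, which also gives that term a definition. State that barrier use not captured on the CRF remains uncorrected.

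The cost is a few lines of text and one derivation. The downside is slightly fewer cycles and a slightly wider, less favourable interval. The correction will be incomplete to the extent that barrier use was not recorded.

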4.1.6 Pearl Index

Pearl Index is defined as the number of on-treatment pregnancies per 100 women years. On -treatment pregnancy is defined as the estimated conception date being on or after the insertion date (must be a successful insertion) and no more than 7 days after the study device is removed or expelled. One women year is defined as comprising thirteen 28-day cycles.

$$\text{Point estimate of Pearl Index: } x \times \frac{1300}{E}$$

where x is the number of on-treatment pregnancies and E is the number of 28-day evaluable exposure cycles

If ETYPE is B or D or E or F, then PREGNANCY = 1; else PREGNANCY = 0

x = sum of PREGNANCY

E = Number of Evaluable Cycles (NCYCEV)

4.1.7 Adverse Event

4.1.7.1 Definition of an Adverse Event

An AE is any untoward medical occurrence in a clinical investigation where a subject has been administered an investigational product and which does not necessarily have a causal relationship with this treatment.

The analysis of AEs will be based on the principle of treatment emergence. Treatment-emergent AEs (TEAEs) will be defined as events that occur (or worsen) on or after the first treatment date of the insertion of the device.

In this study, Pregnancy is an outcome, and not an AE.

4.1.7.2 Definition of a Serious Adverse Event

A serious adverse event (SAE) is any AE occurring within the timelines specified in the protocol that results in any of the following outcomes:

- Death;
- Life-threatening situation (subject is at immediate risk of death);
- Inpatient hospitalization or prolongation of existing hospitalization;
- Persistent or significant disability/incapacity;
- Congenital anomaly/birth defect in the offspring of a subject who received study device; or
- Important medical events that may not result in death, be immediately life threatening, or require hospitalization. Events may also be considered an SAE when, based upon appropriate medical judgment, they may jeopardize the subject and may require medical or surgical intervention to prevent one of the outcomes listed in this definition.

4.1.7.3 Adverse Events of Specific Interest

Adverse events of particular clinical importance (other than SAEs) will be classified as AEs of specific interest (AESIs). For this study, AESIs refer to reports of pain during insertion, pelvic infection (e.g., pelvic inflammatory disease or endometritis), dysmenorrhea, abdominal pain, expulsion, and uterine perforation. AESIs will be identified and assessed by the Medical Monitor during the ongoing monitoring of safety data during the trial, and for the CSR. For each AESI, a narrative may be written and included in the CSR.

4.1.7.4 Adverse Event Relationship to Study Treatment

The relationship of an AE to the drug will be assigned as one of following relationships: not related, unlikely related, possibly related, probably related, and related.

For analysis purposes, “possibly related,” “probably related,” and “related” to an investigational medical product are considered adverse reactions and will be reported as “Related.”

“unlikely related” and “not related” do not qualify as a causal relationship and will be reported as “unrelated”.

A missing relationship will be imputed as “related”.

4.1.7.5 Adverse Events Related to Study Procedures

Adverse events that occur during the study device placement procedure or removal procedure will be reported on the AE case report form and will be assigned one of the relationships noted in Section 4.1.7.4 by the study Investigator. Any missing relationships will be imputed as “related to the study device placement procedure”.

4.1.7.6 Adverse Event Severity

The study investigator will assess the severity of the AE, and severity will be assigned one of the following values: Mild, Moderate, Severe, Life-threatening, or Fatal.

For analysis purposes, Fatal or Life-threatening will be coded as Severe; missing severity will be imputed as Severe.

4.1.8 Imputing Missing or Incomplete Dates of Adverse Events and Concomitant Medications

The most conservative approach will be systematically considered. If the AE onset date is missing or incomplete, it is assumed to have occurred during the study treatment phase (i.e., considered a TEAE) except if the partial onset date or other data, such as the stop date, indicates differently. Similarly, a medication with partial start and stop dates could be considered as both a prior and concomitant treatment.

The following algorithms will be applied to missing and incomplete start and stop dates:

Start Dates

- If the day portion of the start date is missing, then the start date will be estimated to be equal to the date of first insertion, provided the start month and year are the same as the first insertion and the stop date is either after the first insertion or completely missing. Otherwise, the missing day portion will be estimated as "01."

- If both the day and month portions of the start date are missing, then the start date will be estimated to be equal to the date of first insertion, provided the start year is the same as the first insertion and the stop date is either after the first insertion or completely missing. Otherwise, the event will be assumed to start on the first day of the given year (e.g., ??-??-2013 is estimated as 01-JAN-2013).
- If the start date is completely missing and the stop date is either after the first insertion or completely missing, the start date will be estimated to be the day of first insertion. Otherwise, the start date will be estimated to be the first day of the same year as the stop date. All other non-AE and non-concomitant medication day calculations where only partial dates are available will be handled as follows: the first day of the month will be used in the calculations if the day part of a start date is missing, and January 1 will be employed if both the month and day parts of a start date are missing.

Stop Dates

- If only the day of resolution is unknown, the day will be assumed to be the last of the month (e.g., ??-JAN-2013 will be treated as 31-JAN-2013).
- If both the day and month of resolution are unknown, the event will be assumed to have ceased on the last day of the year (e.g., ??-??-2013 will be treated as 31-DEC-2013).
- If the stop date is completely missing or the event is continuing, the event will be assumed to be after first insertion and will be imputed using the last known date on the study.

